5.3. Rationale for Dose and Schedule Selection

Results of the Phase 1/2a study (Study SYN-FIXFc-07-001) evaluating the safety and PK of a single dose of rFIXFc suggested that rFIXFc is well tolerated when given as a single dose at doses ranging from 1 to 100 IU/kg. In the completed Phase 3 study (Study 998HB102), multiple doses between 20 and 100 IU/kg were generally well tolerated, with an AE profile generally consistent with that expected in patients with hemophilia B. No dose-limiting toxicity (DLT) has been identified to date in humans receiving a dose of rFIXFc up to 100 IU/kg.

The recommended starting prophylactic dose of rFIXFc in this study, approximately 50 IU/kg weekly, is based on the data from the Phase 1/2a and Phase 3 studies (including pediatric PK data from subjects <12 years of age) and knowledge of increased clearance of factor concentrates in children (Table 1). This dose is predicted to maintain trough levels >1% in 99% of pediatric subjects. Adjustments to the dose and interval of rFIXFc can be made in this study based on available PK data, subsequent FIX activity levels, level of physical activity, and bleeding pattern, in accordance with local standards of care for a prophylactic regimen.

The dose for treatment of bleeding episodes will target peak plasma FIX activity of approximately 30% to 100%, in accordance with local standards (see guidance provided in Appendix A), and taking into account lower rFIXFc recoveries observed in young children (Table 1). Subjects developing positive low titer inhibitors may continue on study at the same or higher dose per injection of rFIXFc at the discretion of the Investigator (see Section 10.2.6.2).

If a subject requires surgery while participating in this study, the subject may be treated with the dose and regimen of rFIXFc deemed appropriate for the type of surgery. All major surgeries will be reported as serious adverse events (SAEs).

5.4. Potential Risks and Benefits

Refer to the current Investigator's Brochure for descriptions of the potential risks and benefits of rFIXFc.

CONFIDENTIAL

The information contained herein may not be used, disclosed, or published without the written consent of Bioerativ
Therapeutics Inc

6. STUDY OBJECTIVES AND ENDPOINTS

6.1. Objectives

6.1.1. Primary Objective

The primary objective of the study is to evaluate the safety of rFIXFc in previously untreated subjects with severe hemophilia B.

6.1.2. Secondary Objectives

The secondary objectives of the study are as follows:

- To evaluate the efficacy of rFIXFc in the prevention and treatment of bleeding episodes in PUPs.
- To evaluate rFIXFc consumption for prevention and treatment of bleeding episodes in PUPs.

6.1.3. Exploratory Objectives

The exploratory objective of the study is to evaluate the effect of rFIXFc based on patient-reported outcomes and health resource utilization.

6.2. Endpoints

6.2.1. Primary Endpoint

The primary endpoint of the study is the occurrence of inhibitor development.

6.2.2. Secondary Endpoints

The secondary endpoints of the study are as follows:

- the annualized number of bleeding episodes (spontaneous and traumatic) per subject
- the annualized number of spontaneous joint bleeding episodes per subject
- assessments of response to treatment with rFIXFc for bleeding episodes, using the 4-point bleeding response scale (Investigator assessment for bleeding episodes treated in the clinic; parent or caregiver assessment for all other bleeding episodes)
- the total number of EDs per subject per year
- total annualized rFIXFc consumption per subject for the prevention and treatment of bleeding episodes

CONFIDENTIAL

The information contained herein may not be used, disclosed, or published without the written consent of Bioverativ Therapeutics Inc

- the number of injections and dose per injection of rFIXFc required to resolve a bleeding episode
- rFIXFc incremental recovery

6.2.3. Exploratory Endpoints

The exploratory endpoints include, but are not limited to:

- health outcomes

CONFIDENTIAL

The information contained herein may not be used, disclosed, or published without the written consent of Bioverativ
Therapeutics Inc

7. STUDY DESIGN

7.1. Study Overview

This is an open-label, single-arm, multicenter study evaluating the safety and efficacy of rFIXFc in previously untreated subjects with severe hemophilia B when used according to local standard of care. For the purpose of this study, a PUP is defined as a subject who has not had prior exposure to FIX concentrates, except for up to 3 injections of commercially available rFIXFc between 28 days prior to the first Screening Visit and the confirmation of eligibility. Following the confirmation of eligibility, administration of commercially available rFIXFc is no longer allowed and only rFIXFc labeled for study use is to be administered (henceforth, the latter supply will be described as rFIXFc study drug, to distinguish it from commercially available rFIXFc). Subjects with a documented plasma FIX activity of $\leq 2\%$ may be enrolled on the basis of local laboratory results and may receive study drug after samples for factor IX activity level and inhibitors have been obtained for testing at the central laboratory. However, any such subject must be withdrawn if the central laboratory screening results indicate factor IX activity level $> 2\%$ or a positive inhibitor. Baseline incremental recovery (IR) assessments described in Section 4.2.1 should be performed as soon as practicable once all eligibility criteria have been met and the subject has been enrolled. The Baseline IR Visit activities may be completed on the same day as Screening, or they may be completed as a part of a separate visit or at an unscheduled visit.

Following confirmation of eligibility and enrollment, the Investigator has the option to treat a subject episodically (on-demand) prior to initiating a prophylaxis regimen. The duration of episodic treatment is at the Investigator's discretion, in accordance with local standard of care. At least 20 previously untreated subjects are planned to complete the study after reaching at least 50 EDs with rFIXFc. One ED is defined as a 24-hour period in which a subject receives 1 or more doses of rFIXFc, with the time of the first injection of rFIXFc defined as the start of the ED.

Surgery is allowed during the study. See Section 10.2.7 for further instructions.

Immune tolerance induction (ITI) with rFIXFc is allowed during the study for those subjects developing, after exposure to rFIXFc study drug, a positive low titer inhibitor (≥ 0.60 and < 5.00 Bethesda unit [BU]/mL) with bleeding episodes that cannot be adequately treated with rFIXFc, or a positive high titer inhibitor (≥ 5.00 BU/mL). See Section 10.2.6 for further instructions.

Because of the risk of allergic reactions with FIX concentrates, the first administration of rFIXFc (commercially available rFIXFc and/or study drug) must be performed under medical observation where proper medical care for allergic reactions could be provided. The first injection of rFIXFc study drug after the confirmation of eligibility must be administered by the Investigator or a qualified delegate. Thereafter, study drug may be administered by a parent/caregiver, a qualified medical professional under the direction of the Investigator, self-administered by older children, or given at the clinic. Study treatment may also be injected in the hospital, for example, during surgery or during hospitalization due to major bleeding.

CONFIDENTIAL

The information contained herein may not be used, disclosed, or published without the written consent of Bioerativ
Therapeutics Inc

See [Figure 1](#) for a schematic of the study design and [Section 4.2](#) for a description of each study visit and the required assessments. [Section 10](#) describes the treatment of subjects during the study.

7.2. Study Specifics

7.2.1. Dose-Limiting Toxicity

No DLT has been identified to date in humans receiving doses of rFIXFc up to 100 IU/kg. Also, no DLTs were observed in the preclinical animal studies where repeat doses of up to 1000 IU/kg were evaluated. The dose for treatment of bleeding episodes will target peak plasma FIX activity of approximately 30% to 100%, in accordance with local standards (see guidance provided in [Appendix A](#)), and taking into account lower rFIXFc recoveries observed in young children ([Table 1](#)).

7.3. Overall Study Duration and Follow-Up

The study period will consist of screening, treatment, and follow-up. Individual subject study participation is expected to be approximately 6 months to 3 years including screening and follow-up. Each subject is considered to have completed their treatment period once they have reached at least 50 EDs to the study treatment, unless withdrawal from the study occurs, or the end of study is declared. EDs are defined as in [Section 7.1](#).

See [Figure 1](#) for a schematic of the study design.

7.3.1. Screening and Baseline Incremental Recovery Visits

Parents/legal guardians of subjects must be provided with the informed consent information prior to the Screening Visit to allow adequate time for review and an opportunity to discuss the study with the Investigator/designee. After reviewing, parents/legal guardians and subjects will come into the clinic to sign the informed consent/assent; then subjects will undergo screening.

Screening assessments to determine subject eligibility for the study will be collected within 8 weeks after the first Screening Visit (i.e., the first visit for any activity other than informed consent, which can occur prior to the subject's birth), see [Section 4.2.1](#). As part of the screening process, the Investigator must have sufficient documentation of a subject's medical history to ensure previously untreated status.

If more than 8 weeks elapse and screening activities have not been completed, the inhibitor and factor IX activity blood draws must be repeated. Other screening assessments that have not yet been completed must be completed within an additional 8 weeks.

Potential subjects may be enrolled and receive study drug as long as they meet the minimum criteria for enrollment ([Section 8.3](#)), including factor IX activity $\leq 2\%$ from the local laboratory (either at Screening or documented in the medical record) and collection of samples for inhibitor and factor IX activity testing at the central laboratory. If results from central laboratory testing of

CONFIDENTIAL

The information contained herein may not be used, disclosed, or published without the written consent of Bioerativ
Therapeutics Inc

the screening samples for inhibitor and factor IX activity subsequently reveal a factor IX activity level >2% or a positive inhibitor, the subject must be withdrawn.

The Baseline IR Visit assessments should be performed as soon as practicable once all eligibility criteria have been met and the subject has been enrolled. The Baseline IR Visit activities (Section 4.2.1) may be completed on the same day as Screening, or they may be completed as part of a separate visit or at an unscheduled visit. Baseline IR assessments must be performed when the subject is in a non-bleeding state, after at least a 72 hour washout. Eligible subjects will report to the study site for administration in the clinic of the Baseline IR Visit dose of 50 IU/kg by actual potency (see the Directions for Handling and Administration [DHA] and Section 10.1.1 of this protocol for further information on actual potency dosing). The dose will be delivered via a slow push IV injection over several minutes, at a rate of administration determined by the subject's comfort level. Subjects will be required to complete the assessments according to Section 4.2.1, including collection of FIX activity samples for the calculation of incremental recovery.

Bleeding episodes that occur prior to meeting all eligibility criteria should be treated with commercially available rFIXFc. If a subject requires more than 3 injections of commercially available rFIXFc prior to confirmation of eligibility, the subject will be considered a screen failure. In countries where rFIXFc is not yet commercially available, any bleeding episode that occurs prior to meeting eligibility criteria should be treated with another FIX concentrate and the subject will be considered a screen failure. After meeting eligibility criteria, all bleeding episodes should be treated with rFIXFc study drug. The Baseline IR Visit may be delayed until the subject is in a non-bleeding state and a 72-hour washout period may be safely performed.

7.3.2. Treatment

Following confirmation of eligibility and enrollment, the Investigator has the option to treat the subject with an episodic regimen for a period of time before initiating a prophylaxis regimen. The duration of the episodic period is at the Investigator's discretion, in accordance with local standard of care. However, given global standards of care, it is expected that the prophylactic regimen will be initiated prior to or immediately following a third episode of hemarthrosis.

The date of transition from episodic treatment to a prophylaxis regimen must be captured on the electronic case report form (eCRF). The recommended starting prophylactic regimen is 50 IU/kg weekly, although adjustments to the dose and dosing interval of rFIXFc can be made based on available PK data, subsequent FIX activity levels, level of physical activity, and bleeding pattern, in accordance with local standards of care for a prophylactic regimen. Treatment will continue until the subject has reached at least 50 EDs to rFIXFc. Parents/caregivers, or children capable of self-injection, will be instructed on how to administer rFIXFc at home.

Following confirmation of eligibility and enrollment, subjects will report to the study site for 2 kinds of required visits during the Treatment Period:

- Scheduled Interim Visits: every 12 (\pm 2) weeks after enrollment, by calendar date (Section 4.2.2.1).

CONFIDENTIAL

The information contained herein may not be used, disclosed, or published without the written consent of Bioerativ
Therapeutics Inc

- ED Milestone Visits: at 5 (± 2) EDs, 10 to 15 EDs, 20 to 25 EDs, and 50 to 55 EDs (Section 4.2.2.2).

In addition to scheduled clinic visits, telephone calls with the subject's parents/caregivers are planned approximately once a month for study site staff to check on each subject's status.

Additional unscheduled visits may be necessary during the study to test for inhibitors, test for recovery, repeat safety assessments, repeat any blood sampling if required for study purposes or for local standard of care, or perform PK assessments if needed for surgical planning or adjustment of dosing regimen. Investigators are to report all inhibitor assessments performed throughout the study on the eCRF.

Subjects who develop inhibitors may be eligible for 24 months of Immune Tolerance Induction Therapy (ITI) (Section 4.2.4 and Section 10.2.6).

7.3.3. Post-Treatment Follow-Up

Subjects will perform the assessments of the Early Termination (ET)/End of Study (EOS) Visit after at least 50 EDs to rFIXFc has been achieved, if they have withdrawn from the study, or the end of study is declared. A Final Safety Follow-up Visit/Telephone Call will be conducted 14 (+7) days after the last dose of rFIXFc to assess the subject's status for AEs, SAEs, and concomitant treatments and procedures. It will be at the discretion of the Investigator to conduct the Final Safety Follow-up Visit by telephone or in person.

7.4. Study Stopping Rules

Bioverativ may terminate this study at any time, after informing Investigators. Investigators will be notified by the Sponsor or designee if the study is suspended, stopped, or closed.

Study stopping is required for the following:

- unacceptable inhibitor incidence as determined by the Data Safety Monitoring Committee (DSMC; see Section 19.2)
- detection of an unexpected, serious, or unacceptable risk to the study subjects

Data regarding frequency of inhibitor development will be reviewed by the DSMC at regular intervals. If, after consideration of subject-specific risk factors (e.g., genotype), the DSMC judges that the observed rate of inhibitor formation is unacceptable, compared with that reported for commercially available rFIX concentrates, the study will be stopped.

If the study is stopped, the events will be investigated, enrollment will be stopped, and current subjects will stop dosing with rFIXFc. If, in consultation with the DSMC, it is determined that the study should be permanently discontinued, then subjects will attend a final visit.

CONFIDENTIAL

The information contained herein may not be used, disclosed, or published without the written consent of Bioverativ Therapeutics Inc

7.5. End of Study

The end of the study (EOS) will occur when at least 20 subjects have reached at least 50 EDs with rFIXFc. Once this milestone has been achieved, all ongoing study subjects will be required to return to the study center for the Early Termination (ET)/End of Study (EOS) Visit assessments.

The end of treatment for individual subjects is described in Section [10.6](#).

CONFIDENTIAL

The information contained herein may not be used, disclosed, or published without the written consent of Bioverativ
Therapeutics Inc

8. SELECTION OF SUBJECTS

8.1. Inclusion Criteria

To be eligible to participate in this study, candidates must meet the following eligibility criteria at the time of screening, or at the timepoint specified in the individual eligibility criterion listed:

1. Ability of the subject or the subject's legally authorized representative (e.g., their parent or legal guardian) to understand the purpose and risks of the study and provide signed and dated informed consent and authorization to use confidential health information, and/or to provide assent, in accordance with national and local subject privacy regulations.
2. Male, age <18 years at the time of informed consent.
3. Weight ≥ 3.5 kg.
4. Severe hemophilia B defined as ≤ 2 IU/dL ($\leq 2\%$) endogenous FIX documented with local laboratory results either in the medical record or as tested during the Screening Period. Any subject who is enrolled based on results of the local laboratory (from the medical record or at screening) must be withdrawn if the central laboratory screening results indicate a baseline FIX activity level $>2\%$ of normal.

8.2. Exclusion Criteria

Candidates will be excluded from study entry if any of the following exclusion criteria exist at Screening, or at the timepoint specified in the individual criterion listed:

1. History of positive inhibitor testing. A prior history of inhibitors is defined based on a patient's historical positive inhibitor test using the local laboratory Bethesda value for a positive inhibitor test (i.e., equal to or above lower limit of detection).
2. History of hypersensitivity reactions associated with any rFIXFc administration.
3. Exposure to blood components or injection with a FIX concentrate (including plasma derived) other than rFIXFc.
4. Injection with commercially available rFIXFc more than 28 days prior to Screening.
5. More than 3 injections of commercially available rFIXFc prior to confirmation of eligibility.
6. Other coagulation disorder(s) in addition to hemophilia B.
7. Any concurrent clinically significant major disease that, in the opinion of the Investigator, would make the subject unsuitable for enrollment (e.g., HIV infection with

CONFIDENTIAL

The information contained herein may not be used, disclosed, or published without the written consent of Bioerativ
Therapeutics Inc

CD4 lymphocyte count <200 cells/ μ L or a viral load >200 particles/ μ L, or any other known congenital or acquired immunodeficiency).

8. Current systemic treatment with chemotherapy and/or other immunosuppressant drugs. Use of steroids for treatment of asthma or management of acute allergic episodes or otherwise life-threatening episodes is allowed. Treatment in these circumstances should not exceed a 14-day duration.
9. Participation within the past 30 days in any other clinical study involving investigational treatment.
10. Current enrollment in any other clinical study involving investigational treatment.
11. Inability to comply with study requirements.
12. Other unspecified reasons that, in the opinion of the Investigator or Bioverativ, make the subject unsuitable for enrollment.

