10.2.3.2. Information to be Recorded for Bleeding Episodes

Subjects or their parent/caregiver must be issued with an EPD once eligibility has been confirmed and they have been enrolled; from that point forward, all data regarding bleeding episodes and injections administered for a bleeding episode for doses administered at the subject's home or at locations other than the study site must be entered into the EPD. The incidence of bleeding in this study will be obtained from EPDs, eCRFs, and medical records. If a subject has enrolled in the study, information from medical records on dosing and bleeding episodes treated with commercially available rFIXFc prior to the subject being issued with an EPD should be recorded in the eCRF, according to the eCRF Completion Guidelines.

It is recommended that subjects or parents/caregivers enter bleeding episode information into the EPD immediately after an injection.

The Investigators and Clinical Monitors will ensure that there is consistency in bleeding episode data between the subject's medical record, IXRS, source documents, EPD, and eCRFs. During the clinic visits and monthly telephone calls with the subject's parents/caregivers, the subject/parent/caregiver will be reminded about timely EPD completion and the Investigator will verify whether or not a bleeding episode has occurred, and was "spontaneous" or "traumatic" (Section 10.2.3.1).

If, following this discussion, the Investigator judges that the classification by the subject's parents/caregivers was incorrect, the Investigator will document it in the subject's medical records with the rationale for the new classification, and the eCRF, documenting the new classification of the bleeding episode according to the Investigator and whether or not the subject's parents/caregivers agreed with this new classification. With regard to dose changes, the Investigator's classification of spontaneous or traumatic will be used (if different from the classification recorded in the EPD by the parent/caregiver). Both spontaneous and traumatic bleeding episodes will be collected.

Information collected in the EPD will include, but not be limited to, the following:

- the type of bleeding episode (e.g., spontaneous, traumatic) and if related to sports activity or physical activity
- the date the bleeding event occurred
- the dose administered to treat the bleeding episode including any repeat doses
- the location of the bleed

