15.3. Monitoring and Recording Events

15.3.1. Adverse Events

Any AE experienced by the subject between the time of signing of the ICF and the Safety Follow-up Visit is to be recorded on the eCRF, regardless of the severity of the event or its relationship to study treatment.

All AEs experienced by the subject should be followed up until they have resolved, stabilized, or returned to baseline in subsequent visits.

Any adverse event that occurs after the first dose of commercially available rFIXFc but prior to signing of the ICF should be reported as a post-marketing event; such an event will not be recorded in the eCRF.

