### 6.6.1. Exposure

#### 6.6.1.1. Number of Injections and Exposure Days to rFIXFc

For any patient, the total number of days of exposure to rFIXFc will be accumulated from the time of their first on-study injection of rFIXFc. An ED is a 24-hour period in which one or more rFIXFc injections are given. The 24-hour window starts from the first injection on study and then for subsequent injections, it starts from an injection taken after/outside of a previously identified ED.

The total number of EDs on rFIXFc for each patient will be summarized categorically (<5, 5-<10, 10-<20, 20-<50, 50-<75, 75-<100 and >=100) and with descriptive statistics for the Safety Analysis Set.

The total number of injections per patient will be summarized overall and by reason for injection (prophylactic regimen, ITI regimen, spontaneous bleed, traumatic bleed, follow-up injection, surgical and other) using descriptive statistics for the Safety Analysis Set.

These tables will be presented by treatment regimen as described in Section 5.1.1.

The total number of injections and EDs will also be summarized by EPD entry compliance (see Section 6.6.2.3), <80% and >=80%, where >=80% is considered compliant.

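### Children already selected on up to three commercial rFIXFc doses are pooled with naive children, and the SAP drops those doses from the safety set and exposure-day count without listing the change

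*Protocol*

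**What the plan says.** **Entry.** Protocol 7.1 defines a previously untreated patient as one with no FIX concentrate except up to three commercial rFIXFc injections, given between 28 days before first screening and confirmation of eligibility. Section 8.2 excludes "More than 3 injections of commercially available rFIXFc prior to confirmation of eligibility" (criterion 5), and criterion 3 bars blood components and every other FIX concentrate. Criterion 2 excludes a "History of hypersensitivity reactions associated with any rFIXFc administration". Criterion 1 excludes a "History of positive inhibitor testing" and explains: "A prior history of inhibitors is defined based on a patient's historical positive inhibitor test using the local laboratory Bethesda value", with the cut-off at the local limit of detection and no confirmation required. Study drug may start before the central screening result is known. Section 7.1 then says: "However, any such subject must be withdrawn if the central laboratory screening results indicate factor IX activity level". The threshold there is 2%, and an inhibitor in the screening sample has the same consequence. Section 11 repeats the rule.

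**Recording.** Commercial dosing goes into the medical history (Section 4.2.1, footnote d). For enrolled subjects, Section 10.2.3.2 also puts "information from medical records on dosing and bleeding episodes treated with commercially available rFIXFc prior to the subject being issued with an EPD" into the eCRF. Adverse events are recorded from consent onward. For earlier ones Section 15.3.1 states: "Any adverse event that occurs after the first dose of commercially available rFIXFc but prior to signing of the ICF should be reported". The route is post-marketing reporting, outside the eCRF.

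**Analysis.** Protocol 16.5.1 and 16.5.2.1 count commercial rFIXFc in the Safety Analysis Set and in the main inhibitor analysis. SAP 4.2 requires a dose of study rFIXFc, SAP 5.4.5 starts the safety period at the first study dose, and SAP 6.6.1.1 has EDs "accumulated from the time of their first on-study injection of rFIXFc".

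**The concern.** The only FIX exposure allowed before entry is rFIXFc itself, so a reaction or inhibitor after a commercial dose follows exposure to the product under study. These are the events the trial exists to count: inhibitor development is the primary endpoint, and Protocol 7.1, 10.1 and 10.3 treat the first rFIXFc administration, commercial or study, as the point of allergic risk. The entry rules turn such events into ineligibility or withdrawal. Protocol 15.3.2 also says that allergic reactions often occur close in time to inhibitor development, so criterion 2 may remove children at raised inhibitor risk as well.

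At stake is what the reported rate means. A rate labelled as that of previously untreated children would partly describe children who had already passed up to three doses, and no planned table shows how many. The SAP's narrower set and later ED origin make this harder to see.

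**Working it through.** The plan gives no figure for this point: no share pre-exposed, no assumed inhibitor rate, and a sample size (about 30 enrolled, at least 20 reaching 50 EDs) set on clinical grounds. There is nothing to reproduce, so the check compares the two documents and then bounds the effect.

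**1. Protocol against SAP**

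| Item | Protocol | SAP |
|---|---|---|
| Safety Analysis Set | study and/or commercial rFIXFc (16.5.1) | study rFIXFc (4.2) |
| Safety data start | first rFIXFc of either source (16.5.1) | first study dose (5.4.5) |
| ED | any rFIXFc (4.2.2.2, 7.1, 16.5.2.1) | any rFIXFc in 5.2.4; from first on-study injection in 6.6.1.1 |
| Declared in SAP 10 | – | no; it lists only the Full Analysis Set, the dropped Supporting Analysis Set and the questionnaire |

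The SAP is not consistent within itself. Section 9.4.3.2 speaks of the initial rFIXFc administration. Section 5.4.5 starts at study drug yet provides for patients who later fail screening.

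**2. One lost event.** Exact limits for x of n are the 2.5% point of Beta(x, n−x+1) and the 97.5% point of Beta(x+1, n−x), with a lower limit of 0 when x = 0. Adding one excluded event to numerator and denominator:
- 0/30 = 0.0% (0.0 to 11.6) becomes 1/31 = 3.2% (0.1 to 16.7)
- 1/30 = 3.3% (0.1 to 17.2) becomes 2/31 = 6.5% (0.8 to 21.4)
- 2/30 = 6.7% (0.8 to 22.1) becomes 3/31 = 9.7% (2.0 to 25.8)

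**3. Expected effect of the exclusions.** Let f be the share pre-exposed, P the true 50-ED risk, s the share of P that falls in the commercial doses, and q = P·s. Then
- observed risk = (P − fq)/(1 − fq)
- understatement = fq(1 − P)/(1 − fq)
- expected exclusions per 30 enrolled = 30·fq/(1 − fq)

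All inputs are assumptions: f 10–60%, P 3–10%, s 5–30%. At the top of each range, fq = 0.6 × 0.03 = 0.018. The observed risk is 0.082/0.982 = 8.35% against 10%, an understatement of 1.65 points, with 0.55 children excluded. At the bottom, fq = 0.00015, the understatement is 0.01 points and 0.005 children are excluded. Relative understatement over the grid is 0.5% to 17.6%. The exact interval at 1/30 is about 17 points wide.

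**4. ED axis.** If SAP 6.6.1.1 governs the inhibitor analyses, study ED e is true ED e + k, with k at most 3 (three doses on three separate EDs). The Kaplan-Meier estimates at 10, 20 and 50 EDs then describe up to 13, 23 and 53 true EDs for these children. Separately, Protocol 10.6 ends treatment at 50 EDs of rFIXFc, while 10.2.2.2 says 50 EDs of study drug. Under Section 10.6 a child with three commercial EDs could finish at 50 − 3 = 47 SAP EDs and leave the 50-ED denominator.

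**5. Does restarting the count lower the risk?** With cumulative hazard H and k = 3, the true 50-ED risk is 1 − exp(−H(50)). Restart without exclusion gives 1 − exp(−H(53)). Restart with exclusion gives 1 − exp(−[H(53) − H(3)]). Illustrative hazards per ED:

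| Assumed hazard | True | Restart only | Restart with exclusion |
|---|---|---|---|
| 0.001 throughout | 4.88% | 5.16% | 4.88% |
| 0.003 in EDs 1–3, then 0.001 | 5.45% | 5.73% | 4.88% |
| 0 in EDs 1–3, 0.003 to ED 20, then 0.0005 | 6.39% | 6.53% | 6.53% |

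Restart alone never falls below the true value. In these cases restart with exclusion understates the nominal 50-ED risk only where the early hazard is raised, which the documents do not quantify.

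**The case against.** The strongest reply is that this is a reporting matter of small expected size. Commercial doses are optional treatment of bleeds before eligibility. Where rFIXFc is not marketed such a bleed makes the child a screen failure (Protocol 7.3.1), so this is no run-in for everyone. The expected bias in step 3 is far below the sampling error. Not every early event is lost: a child dosed with study drug and then withdrawn on the central screening result stays in either Safety Analysis Set, although withdrawal may come before a confirmatory sample. Under the protocol's set, a consented child who reacts before eligibility could also be counted. All of this stands, and it limits the size of the point. It does not make the selection visible, and the SAP's set removes a child who received only commercial doses.

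A reader might infer three stronger things that the documents do not support:
- *That the early exposure is unrecorded.* The dosing is recorded; only adverse events before consent stay out of the eCRF.
- *That the SAP count moves the 5-, 10- and 20-ED blood tests.* Sites schedule these under Protocol 4.2.2.2, which counts any rFIXFc.
- *That restarting EDs lowers the reported risk.* Step 5 shows otherwise, and the primary estimate is a proportion with no ED axis.

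It is also fair that criterion 1 is broader than the endpoint. One local result at the limit of detection excludes, while the endpoint needs two central results of at least 0.60 BU/mL drawn 2 to 4 weeks apart (Protocol 10.2.4). An excluded child is therefore not necessarily an endpoint event.

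**Conclusion.** The point holds in a limited form. The entry rules select on early rFIXFc exposure in those children who had it. Losing true events this way can only lower the estimated inhibitor and hypersensitivity incidence. The amount cannot be computed from the documents; 0.01 to 1.65 points for inhibitors rests wholly on assumed inputs, and no comparable range was derived for hypersensitivity. A single lost inhibitor would nevertheless roughly double a 1/30 result.

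The undeclared conflict between protocol and SAP over the Safety Analysis Set, the safety start and the ED origin is firm and needs no assumption. The shift of up to three EDs is conditional: SAP 9.4.3.3 sets no on-study limit of its own, so applying 6.6.1.1 there is an inference. The SAP also leaves open whether a commercial dose given after consent is on-study. If the shift applies, it misaligns the axis but does not by itself understate cumulative risk.

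**What to change.** 1. Restore the protocol's Safety Analysis Set and safety start in the SAP.
2. For the milestone and Kaplan-Meier inhibitor analyses, count EDs from the first rFIXFc dose of any source, using the eCRF and medical-history records. A child with k commercial EDs enters the risk set at ED k, so the earliest part of the curve rests on children observed from their first dose. This assumes that prior dosing carries no other information about risk. Protocol 10.2.2.2 and 10.6 must be reconciled on which EDs count toward 50.
3. Report the number pre-exposed. Show inhibitor incidence and hypersensitivity separately for subjects with no prior rFIXFc and for those with one to three commercial doses.
4. From the screening log (Protocol 9.1.1), report how many candidates were excluded under criteria 1 and 2 after commercial rFIXFc. Call this a lower bound, because a child never screened is absent from it. Label any add-back estimate as a sensitivity figure, since criterion 1 is broader than the endpoint.

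The cost is SAP wording and two small tables from data already collected. The analysis changes in items 1, 3 and 4 and the ED count in item 2 alter no eligibility rule, treatment or sampling. The downsides are very small subgroups and a possibly less favourable figure. Reactions before consent remain outside the eCRF and are not recovered.
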